3.1.3 Definition of Baseline

Unless otherwise stated, Baseline will be defined as the last measurement prior to the first dose of study drug.

3.1.4 Summary Statistics

Categorical data will generally be summarized with counts and percentages of subjects. The denominator used for the percentage calculation will be clearly defined. Continuous data will generally be summarized with descriptive statistics including n (number of non-missing values), mean, median, standard deviation, minimum, and maximum.

3.1.5 Missing Data

Date Values

In cases of incomplete dates (e.g. AE, concomitant medication, and medical history start and/or stop dates), the missing component(s) will be assumed as the most conservative value possible. For example, if the start date is incomplete, the first day of the month will be imputed for the missing day and January will be imputed for the missing month. If a stop date is incomplete, the last day of the month will be imputed for the missing day and December will be imputed for the missing month. Incomplete start and stop dates will be listed as collected without imputation.

Date imputation will only be used for computational purposes such as treatment-emergent status. Actual data values, as they appear in the original CRFs, will be presented within the data listings.

Non-Date Values

For sensitivity analyses of the primary efficacy endpoint, missing values will be imputed using multiple imputation (see Section 3.4.1). For the analyses of secondary and exploratory efficacy endpoints, no imputation will be made for missing values. Safety data will be used according to availability, with no imputation for missing data.

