#### 8 SAFETY ASSESSMENTS

#### **8.1** Adverse Events

An AE is defined as any untoward medical occurrence in a clinical investigation participant administered a pharmaceutical product, which does not necessarily have a causal relationship with this treatment. An AE can therefore be any unfavorable and/or unintended sign (including an abnormal laboratory finding), symptom, or disease temporally associated with the use of an investigational medicinal product, whether or not related to the investigational medicinal product. All AEs, including observed or volunteered problems, complaints, or symptoms, are to be recorded on the appropriate eCRF.

AEs, which include clinical laboratory test variables, will be monitored and documented from the time of first dose of study drug until Visit 6. Participants should be instructed to report any AE that they experience to the Investigator, whether or not they think the event is due to study drug. Beginning at the date of the first dose of study drug, Investigators should make an assessment for AEs at each visit and record the event on the appropriate AE eCRF.

Wherever possible, a specific disease or syndrome rather than individual associated signs and symptoms should be identified by the Investigator and recorded on the eCRF. However, if an observed or reported sign or symptom is not considered a component of a specific disease or syndrome by the Investigator, it should be recorded as a separate AE on the eCRF. Additionally, the condition that led to a medical or surgical procedure (eg, surgery, endoscopy, tooth extraction, or transfusion) should be recorded as an AE, not the procedure itself.

Any medical condition already present at the date of the first dose of study drug should be recorded as medical history and not be reported as an AE unless the medical condition or signs or symptoms present at baseline change in severity, frequency, or seriousness at any time during the study. In this case, it should be reported as an AE.

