3.5.1 Adverse Events (AEs)

AEs will be categorized by primary system organ class and preferred term as coded using the MedDRA (version 23.0) category designations. Summaries of AEs, including the count and percentage of participants who experience an AE, will be provided.

An overview of treatment-emergent AEs (TEAEs) will be provided including counts and percentages of subjects (and event counts) with the following:

- Any TEAEs overall and by maximum severity
- Any study drug related TEAEs
- Any treatment-emergent serious AEs (TESAEs)
- Any TEAEs leading to discontinuation of study drug
- Any TEAEs leading to death

Listings will be presented specifically for TEAEs, TESAEs and TEAEs leading to discontinuation of study drug.

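### SAP 3.1.5 dates some adverse events with an incomplete start date before the first dose, so they can lose treatment-emergent status

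*SAP*

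**What the plan says.** SAP 3.1.5 covers incomplete start and stop dates for AEs, medications and medical history. Its stated principle is that "the missing component(s) will be assumed as the most conservative value possible". It then gives the only explicit algorithm for start dates: "if the start date is incomplete, the first day of the month will be imputed for the missing day and January will be imputed" for a missing month. On use it says: "Date imputation will only be used for computational purposes such as treatment-emergent status". Listings keep the date as collected.

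Protocol 8.1 fixes the collection window: AEs "will be monitored and documented from the time of first dose of study drug until Visit 6". It also says: "Any medical condition already present at the date of the first dose of study drug should be recorded as medical history", unless the condition changes in severity, frequency or seriousness.

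SAP 3.5.1 has two kinds of AE output. The general one reads: "Summaries of AEs, including the count and percentage of participants who experience an AE, will be provided". The other is restricted to TEAEs: "An overview of treatment-emergent AEs (TEAEs) will be provided including counts and percentages of subjects (and event counts) with the following", covering severity, relatedness, seriousness, discontinuation of study drug and death. Listings follow for TEAEs, serious TEAEs (TESAEs) and TEAEs leading to discontinuation. Neither section defines a TEAE.

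**The concern.** For treatment-emergent status, the cautious choice is to count an event whose timing is uncertain. SAP 3.1.5 does the reverse: it takes the earliest date the known parts allow, which is the date most likely to precede the first dose. It has no floor at first dose and no exception when the known month or year is the same as that of first dose. Because the protocol documents AEs only from first dose, a recorded AE with an imputed onset before dosing is almost always misdated.

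The affected events are concentrated in the calendar month of first dose, when early intolerance would show. The overview and the three listings named in SAP 3.5.1 are built on TEAE status. With 25 participants per group, one participant wrongly dropped moves a group's TEAE incidence by 1/25 = 4 percentage points.

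**Working it through.** The plan gives no figure on this point, so there is nothing to reproduce. The check applies the rule to dates.

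**Inputs from the documents**
- Missing day becomes the 1st; missing month becomes January; no floor (SAP 3.1.5).
- AEs are documented from first dose to Visit 6, Day 113 (Protocol 8.1 and 6.5).
- Dosing runs over Days 1 to 57 (Protocol 5.5.3).
- Protocol Version 3.0 is dated 2 September 2020 and Version 4.0 is dated 14 January 2021 (SAP 3.1.2).

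**Assumptions**
- A TEAE is an AE whose imputed start is on or after first dose.
- First-dose dates and onset days are uniform.
- The enrolment spans below are illustrative.

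**Single cases**
- First dose 15 March 2021, onset 20 March, day missing: imputed 1 March, before first dose, lost.
- Same first dose, onset 10 April, day missing: imputed 1 April, kept.
- Same first dose, only the year 2021 known: imputed 1 January 2021, lost.
- First dose 10 December 2020, onset January 2021, only the year known: imputed 1 January 2021, kept.

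So a day-missing AE is affected only if its onset is in the month of first dose and first dose was not on the 1st. A year-only AE is affected only if its onset is in the year of first dose and first dose was not on 1 January.

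**Share of day-missing AEs affected, 30-day month**

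If first dose is on day d, onset can fall on 31 − d days of the same month. For d = 1 none is misclassified. The mean number of exposed days is

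(29 + 28 + … + 1) / 30 = 435 / 30 = 14.5.

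- Onset uniform over Days 1 to 57: 14.5 / 57 = 25%.
- Onset uniform over Days 1 to 113: 14.5 / 113 = 13%.
- Onset uniform over Days 1 to 29 (early onset): 14.5 / 29 = 50%.

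**Same count with real calendar months**

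| Assumed first-dose dates | Day missing, Days 1–57 | Day missing, Days 1–113 | Year only, Days 1–57 |
|---|---|---|---|
| Calendar 2021 | 26% | 13% | 92% |
| 2 Sep 2020 to 30 Apr 2021 | 26% | 13% | 88% |
| 14 Jan to 30 Apr 2021 | 24% | 12% | 100% |

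For Days 1 to 29 the day-missing share is 47% to 51%. All of these are shares of partially dated AEs, not of all AEs.

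**After the fix**

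With first dose 15 March 2021 and a start recorded only as March 2021, the later of 1 March and 15 March is 15 March, so the event is treatment-emergent. The same holds for every compatible partial date, so the misclassified share falls to 0%.

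**The case against.** Several points on the other side stand and limit the scope.

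- A reader might infer that all partially dated on-treatment AEs drop out. They do not: later-month onsets with a missing day, and later-year onsets with only a year, keep their status.
- The loss depends on a TEAE definition that the SAP does not give.
- A reader might infer that the rule can only remove events. That cannot be shown without an end to the TEAE window. Suppose the window closes at last dose, last dose is 10 May, and an AE of 20 May is recorded only as May. The rule dates it 1 May and brings it in.
- A reader might infer that the safety endpoint itself is lost. SAP 2.3.4 names AE incidence, and the general summaries in SAP 3.5.1 are not worded as TEAE-only, so they may still count these events. SAP 6 also lists all available data.
- Missing data are queried with sites (Protocol 10.1.5) and AEs are assessed at every visit from Day 1, so year-only dates should be rare.
- Safety is descriptive and the rule is the same in all four groups.

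A reader might also extend the argument to back-dated lipid-altering therapy and the loss of a valid Day 57 LDL-C. SAP 3.2.2 does not say that imputed dates decide which efficacy values are removed, so the documents do not support that step.

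Two further defences do not succeed. The algorithm is introduced as an example, and programming details are deferred to a separate document (SAP 6). But it is the only algorithm stated for start dates and is tied by name to treatment-emergent status, so it is what a programmer would implement. Site queries reduce the number of partial dates but do not change how the remaining ones are handled.

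**Conclusion.** The point holds in a limited form. Followed as written, the rule gives the wrong treatment-emergent status to a definable subset of AEs, against the SAP's own principle and the protocol's collection window. This is an error in a stated rule rather than missing detail.

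Under uniform first-dose days and onsets, about one in four day-missing AEs is misclassified if onsets spread over the dosing period, and about one in eight if they spread over the whole collection period. For year-only dates the share is roughly 88% to 100% over Days 1 to 57, depending on the assumed enrolment dates. The effect on the TEAE tables cannot be sized, because the documents do not say how many AE dates will be incomplete. With few partial dates it will be small. The change should be made because it is cheap and the present rule is wrong for this purpose.

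**What to change.** In SAP 3.5.1, define a TEAE, including where the window ends. In SAP 3.1.5, replace the start-date rule for AEs with text to this effect: if the known parts of the start date are compatible with onset on or after first dose, and the stop date is not before first dose, impute the start as the later of the earliest possible date and the first-dose date, and count the event as treatment-emergent. Listings continue to show the date as collected.

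The cost is about one paragraph of SAP text and one derivation in the AE analysis dataset. The downside is that TEAE counts may be slightly higher.

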# 9.2.1.2 Secondary and exploratory efficacy analysis

A similar MMRM model will be used for the analysis of the secondary and exploratory efficacy endpoints corresponding to the percent change from baseline. For the binary efficacy endpoints, a logistic regression analysis will be performed with model covariates of treatment group and baseline LDL-C.

In order to maintain the overall Type I error rate, the secondary efficacy endpoints will be tested sequentially at the 0.05 significance level according to the pre-specified order of hierarchy. No adjustment will be made for multiplicity in testing the exploratory efficacy endpoints. Nominal p-values will be provided when applicable. Descriptive and graphical summaries by treatment group will also be presented. Any additional sensitivity and/or supplemental analyses will be defined in the SAP.

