2.3.3 Exploratory Efficacy Endpoints

The exploratory efficacy endpoints include the following:

- Percent change from Day 1 to Day 57 in ApoB for the ezetimibe monotherapy group compared to the placebo group;
- Pairwise comparisons among the various treatment groups for the percent change from Day 1 to Day 57 in non-HDL-C, VLDL-C, HDL-C, TG, ApoE, and HDL-ApoE (with and without ApoC3);
- Pairwise comparisons among the various treatment groups for the proportion of participants at Day 57 that achieve LDL-C <2.6 mmol/L (<100 mg/dL), LDL-C <1.8 mmol/L (<70 mg/dL), and LDL-C <1.3 mmol/L (<50 mg/dL);

NewAmsterdam Pharma BV	CONFIDENTIAL	Statistical Analysis Plan
Protocol TA-8995-303		Version V2.0, 24 June 2021

- Pairwise comparisons among the various treatment groups for the change from Day 1 to Day 57, Day 1 to Week 12, and Day 1 to Week 16 in the mean trough plasma levels of obicetrapib; and
- Pairwise comparisons among the various treatment groups for the change from Day 1 to Day 57, Day 1 to Week 12, and Day 1 to Week 16 in CETP mass.

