The primary efficacy analysis of the percent change from Day 1 to Day 57 in LDL-C will be performed using a mixed model for repeated measures (MMRM) approach. The analysis will include fixed effects for treatment, visit, and treatment-by-visit interaction, along with a covariate of the Baseline value as a continuous covariate. It is to note that randomization was stratified by categories of LDL-C value (<3.5 mmol/L [<135 mg/dL] or \ge 3.5 mmol/L [\ge 135 mg/dL]) only to ensure similar distribution of LDL-C across all treatment groups; however, the MMRM model will include the original scale of the LDL-C value as a continuous covariate. The Restricted Maximum Likelihood estimation approach will be used with an unstructured covariance matrix. The least squares means, standard errors, and 2-sided 95% confidence intervals for each treatment group, for the pairwise comparisons of the combination therapy, obicetrapib monotherapy, and ezetimibe monotherapy to placebo, and for the pairwise comparisons of combination therapy and obicetrapib monotherapy versus ezetimibe monotherapy will be provided. The treatment comparison will be performed using a 2-sided test at the $\alpha = 0.05$ level of significance.

The MMRM approach will include all available assessments of percent change in LDL-C from Baseline to Day 29, Day 57, and Day 85. The model assumes the data are missing at random (MAR). If any data are missing, the model will use all information from the other time points to estimate the mean treatment difference at the given time point. No imputation of missing data will be performed for the primary efficacy endpoint analysis.

The analysis will be implemented using SAS[®] Proc Mixed. The sample SAS code can be found below:

Note: USUBJID = unique subject identifier TREATMENT = 0 (Placebo), 1 (Ezetimibe monotherapy), 2 (Obicetrapib monotherapy), 3 (Combination therapy) VISIT = visit BASE = Baseline value PCHG = Percent change from Baseline proc mixed; class USUBJID TREATMENT VISIT; model PCHG = TREATMENT VISIT; model PCHG = TREATMENT BASE VISIT TREATMENT*VISIT / solution cl; Repeated VISIT / TYPE=UN sub=USUBJID; Ismeans VISIT*TREATMENT / cl diffs; run;

Sensitivity Analysis

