3.4.3 Exploratory Efficacy Endpoints

Similar MMRM models will be used for the following analysis:

- Percent change from Day 1 to Day 57 in ApoB for the ezetimibe monotherapy group compared to the placebo group;
- Pairwise comparisons among the various treatment groups for the percent change from Day 1 to Day 57 in non-HDL-C, VLDL-C, HDL-C, TG, ApoE, and HDL-ApoE (with and without ApoC3);
- Pairwise comparisons among the various treatment groups for the change from Day 1 to Day 57, Day 1 to Week 12, and Day 1 to Week 16 in the mean trough plasma levels of obicetrapib; and
- Pairwise comparisons among the various treatment groups for the change from Day 1 to Day 57, Day 1 to Week 12, and Day 1 to Week 16 in CETP mass.

The proportion of subjects at Day 57 that achieve LDL-C <2.6 mmol/L (<100 mg/dL), LDL-C <1.8 mmol/L (<70 mg/dL), and LDL-C <1.3 mmol/L (<50 mg/dL) will be examined through Logistic Regression Models for binary variables with covariates of the treatment groups and the Baseline variable.

The Logistic Regression Model will be implemented using SAS[®] Proc LOGISTIC. The sample SAS code can be found below:

NewAmsterdam Pharma BV	CONFIDENTIAL	Statistical Analysis Plan		
Protocol TA-8995-303		Version V2.0, 24 June 2021		

Note: USUBJID = unique subject identifier TREATMENT = 0 (Placebo), 1 (Ezetimibe monotherapy), 2 (Obicetrapib monotherapy), 3 (Combination therapy) BASE = Baseline value LDLC100 = LDL_C value less than 100mg/dL at DAY57 (YES/NO) for example proc logistic data= LDL_C; Class TREATMENT(ref=0) / Param= Ref; Model LDLC100 = TREATMENT BASE / alpha=0.05 expb plcl plrl orpvalue lackfit; Ods output ParameterEstimates= Log_LDLC100_ParameterEstimates CLoddsPL= Log_ LDLC100_OddsRatios ; Run;

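### The LDL-C target analyses keep only participants with a Day 57 value and ignore the Day 29 LDL-C of the rest, which the MMRM for LDL-C percent change uses

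*SAP*

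**What the plan says.** The targets are exploratory endpoints, listed in SAP 2.3.3 as "Pairwise comparisons among the various treatment groups for the proportion of participants at Day 57 that achieve LDL-C <2.6 mmol/L (<100 mg/dL") and likewise for <70 and <50 mg/dL. SAP 3.1.5 sets the missing-data rule for them: "For the analyses of secondary and exploratory efficacy endpoints, no imputation will be made for missing values". Under SAP 3.4.3 they "will be examined through Logistic Regression Models for binary variables with covariates of the treatment groups and the Baseline variable", and the sample code has the single statement "Model LDLC100 = TREATMENT BASE". There is no Day 29 term and no repeated-measures structure. Protocol 9.2.1.2 names the same kind of model and gives no missing-data rule for it.

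The MMRM text in SAP 3.4.1 treats LDL-C percent change differently. "The MMRM approach will include all available assessments of percent change in LDL-C from Baseline to Day 29, Day 57, and Day 85", and "If any data are missing, the model will use all information from the other time points", under missing at random.

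Four other provisions matter:
- SAP 3.2.2 makes mITT the primary population for every efficacy endpoint. Membership does not require a Day 57 value; that condition belongs to the Per-Protocol Population (SAP 3.2.3).
- SAP 3.2.2 also removes efficacy values obtained after restricted lipid-altering therapy.
- SAP 3.1.2 assigns an early-termination visit on Days 44 to 71 to Day 57, and one on Days 2 to 43 to Day 29.
- SAP 3.4 provides Friedewald LDL-C at each scheduled visit, but ultracentrifugation LDL-C only at Day 1 and Day 57.

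**The concern.** Not imputing costs little where an MMRM follows, because under missing at random the likelihood draws on the other visits. The single-visit logistic model has no such mechanism. A participant with a Day 29 LDL-C and no Day 57 analysis value informs the percent-change estimate and leaves both numerator and denominator of the target proportion. The same measurements are therefore analysed under two missing-data assumptions, and the target analysis takes on part of the Per-Protocol restriction while being labelled mITT.

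At stake is the reading of an easily quoted percentage. Protocol 4.5 rules out replacing withdrawals and arms have about 25 participants, so a few missing values count. The route to bias is missingness linked to response, for example through poor adherence or through values removed after restricted lipid therapy. All planned imputation and all four sensitivity analyses concern the primary endpoint, so nothing is planned on the target scale.

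**Working it through.** **1. The plan's own figure.** SAP 2.2.4 gives power above 90% for a 30-point difference, SD 15, 25 per arm, two-sided 0.05. The noncentrality is 30 / (15 × √(2/25)) = 7.07, and power exceeds 99.99%. The bound is met and is not in dispute; it concerns the primary endpoint and does not bear on the targets.

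**2. Bounds that need no model.** With m of 25 missing and r observed at target, the proportion among all 25 lies between r/25 and (r + m)/25. Each missing value leaves 1/25 = 4 points undetermined.
- m = 3: observed 15/22 = 68%; range 15/25 = 60% to 18/25 = 72%.
- m = 5: observed 14/20 = 70%; range 14/25 = 56% to 19/25 = 76%.

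**3. Size of bias in one arm (combination, <70 mg/dL).** Inputs:
- Mean change −55.5%: 1 − (1 − 0.453)(1 − 0.1858) = 0.555, combining the reductions in protocol 1.3 and 1.4 multiplicatively (an assumption).
- SD of percent change 15 (SAP 2.2.4).
- Baseline mean 135 mg/dL, SD 18 (assumed), limited to 100 to 175 after the inclusion criterion.
- Day 29/Day 57 correlation 0.7 (assumed).
- Log-odds of a missing Day 57 value rising by 1 per SD of worse Day 29 percent change (assumed).
- Missing 8% or 16% (assumed; the documents give no rate).

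Large-sample simulation, true proportion 68.5%:

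| Method | 8% missing | 16% missing |
|---|---|---|
| Day 57 observed only | 70.3% (+1.8) | 72.0% (+3.5) |
| Imputed from Baseline and Day 29 | 68.5% (0.0) | 68.5% (0.0) |
| Missing counted as not at target | 64.7% (−3.8) | 60.4% (−8.1) |

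With the slope set to zero, the observed-only figure has no bias.

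**4. Other inputs.** Two more cases were simulated: mean change −18.58% with the <100 target, and −45.3% with the <70 target. Missingness depended on Day 29 LDL-C level, with a slope of 1 to 2 per SD. The observed-only excess was 1.2 to 1.9 points at 5% missing, 2.5 to 3.9 at 10%, and 4.9 to 7.7 at 20%. Imputation left about zero bias throughout.

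**5. Odds ratios.** With the step 3 mechanism applied equally in each arm, crude odds ratios moved from true to observed-only as follows:
- <70, combination vs obicetrapib: 2.72 to 2.76 at 8%; 2.74 to 2.81 at 16%.
- <50, combination vs ezetimibe: 186 to 184; 186 to 182.
- <100, combination vs ezetimibe: 46 to 50; 45 to 53. The risk difference at 8% falls from 61.1 to 60.2 points.

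The small differences between the true values at 8% and 16% are simulation error. The direction depends on the threshold and the effect measure.

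**The case against.** The strongest reply is blinding. Protocol 5.3 and SAP 2.2.2 keep participants, investigators, the research organisation and the sponsor blind to all lipid results through the last PK visit, and protocol 4.5 does not list poor lipid response as a reason for withdrawal. Nobody deciding on withdrawal sees the Day 29 LDL-C. This stands, and it makes response-related dropout less likely. It does not exclude an indirect route: poor adherence can lead to both a weak response and withdrawal.

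Three stronger readings are tempting, and the documents do not support them:
- **That the analysis is completers-only.** Protocol 6.6 collects a fasting lipid profile at early termination, and a visit on Days 44 to 71 counts as Day 57. Those lost are participants whose last usable value falls earlier, who have no usable sample, or whose Day 57 value is removed after restricted therapy.
- **That target proportions and odds ratios will be overstated.** The first needs response-related missingness, for which the documents give no figure. The second fails as a general statement at step 5.
- **That counting missing as failure is the correction.** On these inputs it lies further from the truth than the planned method.

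Two further replies stand in part. SAP 3.4.3 does not say whether the targets use Friedewald or ultracentrifugation LDL-C; under the latter there is no Day 29 value to use. And setting the primary MMRM beside the second sensitivity analysis (ANCOVA on observed Day 57 Friedewald values) shows indirectly, on the continuous scale, what dropping these participants does. It gives no corrected target proportion.

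The effect is also small next to sampling error: √(0.684 × 0.316 / 25) = 9.3 points for one arm.

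**Conclusion.** The point holds as an inexpensive improvement to an exploratory analysis; it does not show that the planned analysis is biased. From the text alone, the target models omit mITT participants without a Day 57 analysis value and leave their Day 29 LDL-C unused, while the percent-change MMRM uses it. That comparison assumes the targets are based on Friedewald LDL-C.

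If missingness depends on Day 29 response, the single-arm proportion is too high by about 2 points at 8% missing and 3.5 at 16%. Those sizes rest on the assumed baseline distribution, correlation, dropout slope and missing rates. If missingness is unrelated to response, the bias is zero. The primary result and the secondary testing hierarchy are untouched, and the targets carry nominal p-values only.

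**What to change.** Before unblinding, amend the SAP as follows:
- **3.1.5:** limit the no-imputation sentence to the endpoints analysed by MMRM.
- **3.4.3, source:** state that the targets use Friedewald LDL-C.
- **3.4.3, method:** multiply impute continuous Day 57 LDL-C within arm from Baseline and Day 29, derive the three indicators, fit the logistic model in each data set and combine by Rubin's rules. This matches the MMRM's missing-at-random assumption. Values removed after restricted therapy are treated as missing, as they are in the MMRM.
- **3.4.3, supportive:** keep the observed-case result and print its denominator, as SAP 3.1.4 already promises for percentages.
- **Optional:** one row counting missing as not at target, with all mITT participants in the denominator, labelled a conservative bound.

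The cost is SAP wording and modest programming; no new data are needed. The proportions may come out slightly less favourable than the observed-case figures.
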